#### MONITORING PROCEDURES

[name] assures that informed consent is obtained prior to performing any research procedures, that all subjects meet eligibility criteria, and that the study is conducted according to the IRB-approved research plan.

Study data are accessible at all times for the PI and co-investigators to review. The PI and co-investigators review(s) study conduct accrual, drop outs, deviations from protocol on a semi-annual basis. The PI and co-investigators review(s) AEs individually real-time and in aggregate on a semi-

annual basis. The PI and co-investigators review(s) serious adverse events (SAEs) in real-time. The PI ensures all protocol deviations, AEs, and SAEs are reported to the IRB according to the applicable regulatory requirements.

### COLLECTION AND REPORTING OF SAEs AND AEs

For this study, the following standard AE definitions are used:

**Adverse event:** Any unfavorable and unintended sign (including an abnormal laboratory finding), symptom or disease temporally associated with the use of a medical treatment or procedure, regardless of whether it is considered related to the medical treatment or procedure. Staff will document any occurrence that meets this definition, is a new symptom/condition for the participant, and results in either self-treatment or treatment by a health care provider.

**Serious Adverse Event:** Any AE that results in any of the following outcomes:

- Death
- Life-threatening
- Event requiring inpatient hospitalization or prolongation of existing hospitalization
- Persistent or significant disability/incapacity

AEs are graded according to the following scale:

**Mild:** An experience that is transient, & requires no special treatment or intervention. The experience does not generally interfere with usual daily activities. This includes transient laboratory test alterations.

**Moderate:** An experience that is alleviated with simple therapeutic treatments or minimal, local, and non-invasive intervention. The experience impacts usual daily activities. Includes laboratory test alterations indicating injury, but without long-term risk.

**Severe:** An experience that requires invasive intervention and/or medical attention. The experience interrupts usual daily activities. If hospitalization (or prolongation of hospitalization) is required for treatment it becomes an SAE. A serious adverse event (SAE) is one that meets one or more of the following criteria: results in death; is life-threatening (places the participant at immediate risk of death from the event as it occurred); results in inpatient hospitalization or prolongation of existing hospitalization; results in a persistent or significant disability or incapacity; or results in a congenital anomaly or birth defect.\*

**Life-threatening:** the event is potentially fatal

\*Note: an important medical event that may not result in death, be life threatening, or require hospitalization may be considered an SAE when, based on appropriate medical judgment, the event may jeopardize the participant and may require medical or surgical intervention to prevent one of the outcomes listed in this definition.

The study uses the following AE attribution scale:

**Unexpected or unanticipated:** Unexpected in terms of nature, severity, or frequency given (a) the research procedures that are described in the protocol-related documents, such as the IRB-approved research protocol and informed consent document; and (b) the characteristics of the participant population being studied

**Not related:** The AE is clearly not related to the study procedures (i.e., another cause of the event is most plausible and/or a clinically plausible temporal sequence is inconsistent with the onset of the event).

**Possibly related:** An event that follows a reasonable temporal sequence from the initiation of study procedures, but that could readily have been produced by a number of other factors. There is a reasonable possibility that the incident, experience, or outcome may have been caused by the procedures involved in the research.

**Related:** The AE is clearly related to the study procedures. May suggest that the research places participants or others at a greater risk of harm (including physical, psychological, economic, or social harm) than was previously known or recognized.

AEs are identified during treatment sessions by asking subjects directly if they have experienced AEs. Other research staff may also identify AEs during recruitment calls, scheduling calls, or other conversations with participants.

SAEs and specific procedure-associated AEs are reported to the IRB and sponsor within 24 hours. In addition, all AEs are reported according to the UW IRB AE reporting guidelines.

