### General/Reaction to Assessments

Regarding research risks, participants may experience fatigue and/or boredom while completing the assessments and/or the treatment sessions.

Some participants may also experience mild anxiety, frustration, and/or stress while answering sensitive questions about depression, pain, and mood. As a result of answering questions about pain, some participants may focus more on their pain, which may lead to a temporary increase in pain intensity.

**Protections against risks:** Participants will be informed during the consent process and throughout the study they do not have to discuss any topics they do not wish to during treatment or the assessment periods. In addition, participants will be informed in the consent process they are free to stop any session, treatment, or assessment at any time. Participants are informed they may refuse to answer any questions that make them feel uncomfortable.

All participants will be clearly informed of their right to withdraw from the study at any point without adversely impacting their routine medical, psychiatric, or psychotherapeutic care.

All participants will be offered the opportunity to discuss any situations or experiences associated with the study procedures that they deem uncomfortable or adverse with the UW PI, [name], who is a licensed clinical psychologist. [name] is a trained psychologist who has experience assessing the level of distress of patients and proceeding accordingly whenever an adverse event should arise.

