#### **MANAGEMENT OF RISKS TO SUBJECTS**

##### Expected AEs

Expected AEs associated with the study procedures include:

- Discomfort when talking about pain
- Boredom completing questionnaires

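### The rule that an adverse event is documented only if it is new and treated conflicts with the plan's own AE definition, Mild grade and expected-AE list, and leaves out non-serious worsening of existing pain or mood symptoms

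*Protocol*

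**What the plan says.** Protocol section 10.6 (Collection and Reporting of SAEs and AEs) begins with a broad AE definition: an unfavorable, unintended sign, symptom or disease that is linked in time to the treatment, whatever its cause. The recording rule follows. "Staff will document any occurrence that meets this definition", on condition that it also "is a new symptom/condition for the participant, and results in either self-treatment or treatment by a health care provider".

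Four other places bear on this rule:

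- The grading scale in the same section describes Mild as "An experience that is transient, & requires no special treatment or intervention".
- Section 10.6 (Expected AEs) lists two items: "Discomfort when talking about pain" and "Boredom completing questionnaires".
- Section 10.1 (General/Reaction to Assessments) warns that, after answering questions about pain, "some participants may focus more on their pain, which may lead to a temporary increase in pain intensity". It also names mild anxiety, frustration and stress.
- Section 2.2 makes chronic pain an entry requirement: at least 3 months' duration and an average intensity of at least 3 on a 0-10 scale.

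On use of the records, section 10.6 says that all AEs go to the IRB under its reporting guidelines. It also says that the investigators review AEs one by one and, twice a year, in aggregate.

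**The concern.** The section uses two different ideas of an adverse event. The definition, the grading scale and the expected-AE list all treat minor, untreated experiences as AEs. The documentation sentence then admits only events that are both new and treated. In a trial where everyone enters with chronic pain, the word new also excludes a flare of that pain, which is one of the risks the protocol tells the IRB to expect.

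What is at stake is how the AE count is read. If the rule is followed as written, few Mild events, few expected AEs and no recorded pain flares would be partly a product of the rule. The aggregate AE review would have the same gap, since it can only summarize what was documented. This is separate from how often, or in which arm, participants are asked about AEs: a flare reported in answer to a direct question would still fail the rule.

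**Working it through.** No arithmetic applies, because the documents give no AE rate. The check sets the documentation rule against each class of event that the protocol names.

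Write D for meeting the AE definition, N for being new to the participant, and T for being treated by the participant or a provider. The sentence joins its conditions with 'and', so:

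- AE under the plan's definition: D
- AE that staff document: D and N and T
- Shortfall: events with D that lack N, or T, or both

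The documented set lies inside the defined set, so the recorded count can equal the count under the definition or fall below it. It cannot exceed it.

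| Event class (protocol source) | New? | Treated? | Documented under the rule? |
|---|---|---|---|
| Mild event (10.6, grading scale) | Possibly | Seldom: the grade means that no special treatment was needed | Only if new and self-treated anyway |
| Discomfort when talking about pain (10.6, Expected AEs) | Possibly | Not ordinarily | Not ordinarily |
| Boredom with questionnaires (10.6, Expected AEs) | Possibly | Not ordinarily | Not ordinarily |
| Temporary increase in existing pain (10.1) | No, for every participant (2.2) | Either | No, even if treated |
| Worsening of existing mood symptoms (10.1) | No, where symptoms were already present | Either | No |
| First-onset anxiety, stress or distress (10.1) | Yes | Varies | Only if treated |
| Worsening that meets a serious criterion (10.6) | No | Usually | Fails the sentence as written, but probably captured by the serious adverse event (SAE) route |

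The last row differs because the SAE definition is tied to the AE definition and does not repeat the new-and-treated conditions. SAEs also have 24-hour reporting.

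Nothing else in the documents repairs the middle of the table. No section exempts Mild events, expected AEs or worsening of an existing condition from the rule. Pain intensity and depressive symptoms are collected by questionnaire (5.3), but as outcomes, at baseline and three later assessments (5.1), so a short flare between assessments can be missed. The Statistical Analysis section of the SAP compares means and the proportion with a 10-point decrease in pain interference. It describes no AE analysis and no analysis of participants who got worse.

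**The case against.** A fair defense is that a treatment threshold for logging AEs is a legitimate choice in a low-risk telephone trial. Pain fluctuates in this population, and recording every fluctuation would bring in noise. No aim or hypothesis concerns safety. Worsening is not invisible: both groups complete pain and mood questionnaires, the investigators can see study data at any time (10.6), and supervision of the therapists includes routine assessment of problems (10.1, Treatment). Unfiltered logging could also distort a comparison, because direct questioning about AEs is described only at treatment sessions, so extra minor events would come mainly from the E-TIPS arm.

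Much of this stands. It limits the consequence and adds a condition to the remedy. It does not reconcile the documentation sentence with the Mild grade or the expected-AE list, and the protocol gives no rationale for the threshold.

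A reader might infer more than the documents support:

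- That any worsening of pain or mood is lost. Serious worsening has the SAE route, suicidality has its own protocol, and new, treated low mood would be recorded. Depression is not an entry criterion. Section 1.8 says only that chronic pain is associated with it.
- That the Mild count must be zero. An event that needs no special treatment may still be self-treated.
- That section 10.1 (Mental Health Issues / Suicidality) foresees deterioration caused by the study. It concerns the discovery of existing problems.
- That the two SAE lists in section 10.6 differ in a way that matters here. The second contains the first and adds congenital anomaly, with a discretionary note on important medical events. The repetition is largely editorial.

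**Conclusion.** The point holds for non-serious events. The documentation rule is inconsistent with the AE definition, the Mild grade and the expected-AE list in the same section. It excludes non-serious worsening of existing pain, a class of event open to every participant by eligibility, and of mood symptoms where they were already present. The direction is certain if the rule is followed: the recorded count cannot exceed the count under the plan's own definition, and it falls short whenever an event of an excluded class occurs. The size cannot be derived from the documents.

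This rests on three assumptions:

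- Staff apply the sentence as written. The AE form and session-note rules are not shown, so actual recording may have been wider.
- The two expected AEs would not ordinarily be treated. This is a judgment; the protocol does not say so.
- Some participants have mood symptoms at entry. The documents give no rate.

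**What to change.** Reconcile the documentation sentence with the AE definition, the Mild grade and the expected-AE list. Suggested wording: staff document each occurrence that meets the AE definition and is new, or worse than at baseline, whether or not it was treated; whether it was new or worsened, and any treatment received, are recorded as separate fields. State explicitly that worsening of baseline pain or mood counts, and what separates it from ordinary fluctuation. As a minor tidy-up, keep a single SAE list.

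The cost is one sentence, added form fields, and more minor events to log and review, since each AE is also reviewed individually. While direct questioning is described only at treatment sessions, AE counts should not be compared between arms without noting that difference.

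The SAP already reports 12-week missingness for 202 participants, so changing the rule may no longer be practicable. If data collection is complete, the report should state that only new, treated events were recorded. It should draw no safety conclusion from low counts of Mild or expected AEs, or from the absence of recorded pain flares. That costs a sentence or two.

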#### **MANAGEMENT OF RISKS TO SUBJECTS**

##### Expected AEs

Expected AEs associated with the study procedures include:

- Discomfort when talking about pain
- Boredom completing questionnaires

##### AE Management

Subjects may end any treatment without negative consequences whenever they want.

#### **DATA ANALYSIS PLANS**

Data will be kept in a secure database. Data will be accessed by trained study members. The de-identified data will be reviewed and analyzed by a trained statistician.

#### **PLAN FOR DATA MANAGEMENT**

Compliance of regulatory documents and study data accuracy and completeness will be maintained through an internal study team quality assurance process.

Confidentiality throughout the trial is maintained by the research assistants, coordinators, and PI.

**Training and Fidelity.** [name] will train and supervise the therapists; she is a psychologist with >20 years of expertise in the study populations and intervention. Therapists will receive 20 hours of training in E-TIPS which will include readings, didactic presentations, and practice sessions. [name] will review recorded practice sessions and provide additional training as needed. A fidelity protocol will include protocol checklists of prescribed, proscribed, common, and unique elements; weekly supervision meetings; and ongoing review of randomly selected recordings from 20% of all sessions. If fidelity problems occur, [name] will provide feedback, additional coaching, practice, and monitoring until the therapist delivers the treatment as intended. Similar procedures in past RCTs have yielded fidelity rates exceeding 98%.

**10.7 Un-blinding.** If this is a double-blinded or single-blinded study in which the participant and/or you do not know the group to which the participant is assigned: describe the circumstances under which un-blinding would be necessary, and to whom the un-blinded information would be provided.

**10.8 Withdrawal of participants.** If applicable, describe the anticipated circumstances under which participants will be withdrawn from the research without their consent. Also, describe any procedures for orderly withdrawal of a participant, regardless of the reason, including whether it will involve partial withdrawal from procedures and any intervention but continued data collection or long-term follow-up.

Participants could potentially be withdrawn without consent. In the past this has been very rare. Typically happening in instances where the participant becomes unable to contact despite frequent calls from study staff. PIs also reserve the right to withdraw subjects if they feel it is in their best interest (in cases where procedures could be contributing to suicidal ideation). However, suicidal ideation is not expected to be a risk in this study.

**10.9 Anticipated direct benefits to participants.** If there are any direct research-related benefits that some or all individual participants are likely to experience from taking part in the research, describe them below:

*Do not include benefits to society or others, and do not include subject payment (if any). Examples: medical benefits such as laboratory tests (if subjects receive the results); psychological resources made available to participants; training or education that is provided.*

Previous studies with the therapeutic skills taught in the planned study support their efficacy in reducing pain interference and improving other pain-related outcomes. We anticipate based on this previous research that many of the participants will experience significant reductions in their daily pain interference and other benefits associated with the treatment.

In our past research, many members have expressed satisfaction from receiving treatment in a caring and nonjudgmental environment. Thus, participants in treatment will take away from the study new skills and knowledge regarding chronic pain and how to manage it, and – given previous results of RCTs for psychosocial interventions for chronic pain – should experience some degree of relief from pain and suffering and increases in their quality of life.

**10.10 Individual subjects findings.**

**a. Do you anticipate that the research will produce any urgent, clinically actionable results?**

*These may be results from screening procedures, results that are actively sought for purposes of the study or they may be results that are discovered unintentionally. Examples include high calcium levels, liver function test results, and a mass on an MRI that may indicate a tumor, a diagnostic discrepancy, and suicidal intentions.*

No

Yes

→ If yes, the results should be shared with the subject(s). Complete and upload the [SUPPLEMENT: Participant Results Sharing](#) to the [Supporting Documents](#) SmartForm of [Zipline](#)

**b. Do you plan to share any other results of your study procedures or findings with the subjects – such as genetic test results, laboratory tests, etc.?**

No

Yes

→ If yes, complete and upload the [SUPPLEMENT: Participant Results Sharing](#) to the [Supporting Documents](#) SmartForm of [Zipline](#)

**10.11 Commercial products or patents.** Is it possible that a commercial product or patent could result from this study?

No  
 Yes

→ If yes, describe whether subjects might receive any remuneration/compensation and, if yes, how the amount will be determined.

## 11 ECONOMIC BURDEN TO PARTICIPANTS

**11.1 Financial responsibility for research-related injuries.** Answer this question only if the lead researcher is not a UW student, staff member, or faculty member whose primary paid appointment is at the UW.

Describe who will be financially responsible for research-related injuries experienced by subjects, and any limitations. Describe the process (if any) by which participants may obtain treatment/compensation.

**11.2 Costs to subjects.** Describe any research-related costs for which subjects and/or their health insurance may be responsible (examples might include: CT scan required for research eligibility screening; co-pays; surgical costs when a subject is randomized to a specific procedure; cost of a device; travel and parking expenses that will not be reimbursed).

Because this study requires completion of treatment via telephone it is possible that there is usage of minutes if participant is using a smartphone. Furthermore, if a participant indicates they want text reminders and don't have unlimited texting plans there is a possibility they could be charged messaging fees.

**11.3 Reimbursement for costs.** Describe any costs to subjects that will be reimbursed (such as travel expenses).

None. Researchers are not responsible for any messaging or data charges incurred by participants. If the participant is unable to access the online treatment sessions because of a temporary issue such as a broken smartphone, tablet, computer, or other software or hardware issues, researchers will not be responsible for any costs incurred by participants to fix any of this technology.

## 12 RESOURCES

**12.1 Faculty Advisor.** (For researchers who are students, fellows, or post-docs.) Provide the following information about your faculty advisor.

- Advisor's name
- Your relationship with your advisor (for example: graduate advisor; course instructor)
- Your plans for communication/consultation with your advisor about progress, problems, and changes.

n/a

**12.2 Study team communication.** Describe how you will ensure that each study team member is adequately trained and informed about the research procedures and requirements (including any changes) as well as their research-related duties and functions.

**There is no study team.**

[name] will oversee training of all study team members on the procedures and changes. All study team members are strongly encouraged to read both the sponsor grant proposal, the study protocol, and this IRB application (after it has been approved) before commencing any study-related activities.

Changes to the project (i.e., modifications) will be informed to the study team by email, with specific instructions and links to any new/modified materials. We will also keep a document of changes approved through modification as well as a list of the most up-to-date materials that staff may review for their information. Old materials are archived (both in hard form and electronically) and all documents are labeled with version number and approval date.

The study team will also meet regularly, at least once/week, to review recruitment/enrollment/retention reports, problem-solve any issues that arise, and discuss other study procedures. [name], the PI, will lead these meetings and provide ongoing training and supervision of staff in the study and human subjects research as needed. Our research lab also offers research staff professional development training in the conduct of research and encourages use of ITHS resources, both web-based and workshops.

